A total of 43 participants were initially enrolled between May 2024 and February 2025 from the neurological rehabilitation clinic of the Physical Medicine and Rehabilitation Department at Biruni University Hospital. Following baseline evaluations and BTX-A injections, participants were randomly allocated into two groups: 22 patients in the Mirror Therapy (MT) group and 21 patients in the Sham Therapy (SHA) group. Permuted block randomization was employed to ensure balanced group sizes and reduce selection bias. The randomization sequence was generated using a computer-based random number system and was implemented by an independent researcher not involved in patient assessment or treatment. Group allocation was concealed using sealed, opaque envelopes until the point of assignment.

In the MT group, 4 participants were excluded due to irregular attendance (<75% session compliance), 2 participant withdrew their informed consent, and 1 were hospitalized for unrelated medical conditions requiring inpatient treatment. In the SHA group, 4 participants failed to adhere to the intervention frequency, and 2 were excluded because they received additional pain management therapies during the follow-up period.

Consequently, 15 participants in each group (n = 30 total) completed the full 6-month intervention and follow-up assessments and were included in the final statistical analysis. The overall participant flow, including recruitment, allocation, and attrition, is illustrated in.

The study was conducted according to the approved protocol and completed as planned without early termination. The follow-up period for each participant lasted six months after BTX-A injection, and all post-treatment evaluations were completed by March 2025.

All intervention sessions were delivered by the same licensed physical therapist specialized in neurorehabilitation, ensuring procedural consistency across both groups. Adherence to the

intervention protocol was closely monitored by weekly attendance tracking and therapist supervision to maintain treatment fidelity.

Participants were allocated as follows:

- **Experimental Group (Group I, n=15):** Received mirror therapy in addition to conventional rehabilitation.

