- **Control Group (Group II, n=15):** Received a sham intervention alongside conventional rehabilitation. In this group, a transparent glass panel was used in place of a mirror, and patients were instructed to observe the reflection of their paretic extremity, thereby eliminating the visual illusion effect central to mirror therapy.

A single-blind study design was implemented to minimize bias. Neither the participants nor the outcome assessors were aware of group assignments. Both the mirror therapy and sham interventions were administered by a licensed physical therapist experienced in neurorehabilitation, who was not involved in data analysis or outcome evaluation.

Evaluation Criteria

Treatment efficacy was assessed at two time points: baseline (prior to BTX-A injection) and six months post-injection. The following standardized clinical instruments were employed to evaluate motor function, spasticity, and muscle strength:

Motor Function: Assessed using the Brunnstrom Recovery Stages, with separate scoring for the hand and upper extremity. This scale provides a stage-based evaluation of motor recovery following stroke, ranging from flaccidity (Stage I) to near-normal movement patterns (Stage VI).

Spasticity: Evaluated using the Modified Ashworth Scale (MAS), which quantifies resistance during passive soft-tissue stretching. The MAS scores range from 0 (no increase in muscle tone) to 4 (rigid in flexion or extension), offering a reliable measure of spasticity severity.

Overall Motor Performance: Measured with the Fugl-Meyer Assessment for Upper Extremity (FMA-UE), a validated and widely used tool that evaluates motor function, coordination, and

reflexes in the paretic arm. Scores range from 0 to 66, with lower scores indicating more severe impairment.

Muscle Strength: Quantified using a handheld dynamometer (Jamar® or equivalent) for both the paretic and non-paretic upper extremities. Grip strength (in kilograms) was recorded as the maximum value of three consecutive trials, with standardized positioning to ensure consistency.

All assessments were conducted by a trained physiotherapist ([name]) blinded to group allocation. Standardized testing protocols were followed across all time points to ensure inter-session reliability.

Intervention Protocol

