All participants initiated their rehabilitation and mirror/sham therapy sessions two weeks after the BTX-A injection, coinciding with the onset of the toxin's maximal clinical effect. Adherence to the intervention protocol was strictly monitored throughout the study period.

Statistical Analysis

All statistical analyses were performed using IBM SPSS Statistics for Windows, Version 22.0 (IBM Corp., Armonk, NY, USA). The normality of continuous variables was assessed using the Shapiro-Wilk test. As the data were not normally distributed, non-parametric tests were employed for all comparisons. Continuous variables were expressed as mean \pm standard deviation (SD), and categorical variables were presented as frequencies and percentages. Between-group comparisons at baseline and post-treatment were conducted using the Mann-Whitney U test for continuous variables and the Chi-square test for categorical variables. To evaluate within-group changes from pre- to post-treatment, the Wilcoxon signed-rank test was used. In addition, Spearman's rank-order correlation coefficient (ρ) was calculated to assess the relationships between changes in motor function, spasticity, and muscle strength. A two-tailed p-value < 0.05 was considered statistically significant for all analyses. No corrections for multiple comparisons were applied, as the primary outcomes were pre-specified.

A priori sample size estimation was performed using G*Power software (Version 3.1), assuming a two-tailed test with an effect size of $d = 0.62$, $\alpha = 0.05$, and power $(1-\beta) = 0.80$. A minimum total sample size of 28 participants (13 in one group and 15 in the other) was deemed sufficient to detect statistically meaningful between-group differences.

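### No between-arm test adjusts for the baseline measured before randomisation, so with 15 per arm precision is lost if baseline predicts the six-month score

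*Combined protocol and SAP*

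**What the plan says.** The Statistical Analysis section compares the arms in two separate cross-sections: between-group "comparisons at baseline and post-treatment were conducted using the Mann-Whitney U test for continuous variables and the Chi-square test for categorical variables". It also says that "As the data were not normally distributed, non-parametric tests were employed for all comparisons". The pre-to-post pairing appears in only two other places. One is within each arm: "To evaluate within-group changes from pre- to post-treatment, the Wilcoxon signed-rank test was used". The other is a set of Spearman correlations among the changes in different outcomes, which does not compare arms. No ANCOVA, rank-ANCOVA, stratified test or between-arm test of change is described.

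The baseline is a proper pre-randomisation covariate. Evaluation Criteria gives the timing: "Treatment efficacy was assessed at two time points: baseline (prior to BTX-A injection) and six months post-injection". Study Design and Participants gives the order: "Following baseline evaluations and BTX-A injections, participants were randomly allocated into two groups". The same section gives the analysed numbers: "15 participants in each group (n = 30 total) completed the full 6-month intervention and follow-up assessments", out of 43 randomised.

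**The concern.** A between-arm test at baseline shows whether the arms looked alike; it adjusts nothing. The treatment effect is then tested as if the baseline had not been recorded. If a patient's baseline score predicts the six-month score, the unadjusted test leaves that predictable variation in the noise. With 30 patients, that is information the trial can hardly spare.

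There is a second consequence. The 5% error rate of the unadjusted test is an average over all randomisations. It is above 5% in samples where the arms happen to differ at baseline and below 5% in the others, so its p-value cannot be read in the light of the gap actually seen.

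**Working it through.** **Inputs.** From Statistical Analysis: d = 0.62, two-sided alpha 0.05, planned power 0.80, planned total 28 (13 and 15). From Study Design and Participants: 15 per arm analysed. Assumed, because the documents do not give it: r, shown from 0 to 0.8.

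**1. The plan's own figure.** By the normal approximation, n per arm = 2(1.960 + 0.842)²/0.62² = 40.8, so 41. The t test needs 42 per arm (total 84) and the Mann-Whitney test about 44 (total 88). The stated 28 does not reproduce. With 15 and 15, power at d = 0.62 is 37% (t) or 36% (Mann-Whitney). That is a separate fault, but it sets the starting point here.

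**2. Width of the confidence interval (FMA-UE, grip).** Relative to the unadjusted mean difference, the ANCOVA standard error is √[(1 − r²)(1 + 1/26)] with 15 per arm.
- r = 0: √1.038 = 1.02
- r = 0.3: √(0.91 × 1.038) = 0.97
- r = 0.5: √(0.75 × 1.038) = 0.88
- r = 0.7: √(0.51 × 1.038) = 0.73
- r = 0.8: √(0.36 × 1.038) = 0.61

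The change from 28 to 27 degrees of freedom alters these by under 0.2%. The interval is thus 2% wider at r = 0, and 3%, 12%, 27% and 39% narrower at r = 0.3, 0.5, 0.7 and 0.8. Break-even for the standard error is r² = 1/27, or r = 0.19. In simulated lognormal scores (skewness 1.3 to 6.2), coverage stayed at 95-96% and the width ratios at 0.97-0.98, 0.89-0.90, 0.74-0.75 and 0.62-0.64 for latent r = 0.3 to 0.8.

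**3. Power of the rank tests.** Simulation with 15 per arm. Rank-ANCOVA here means: rank baseline and six-month scores over both arms with mid-ranks for ties, regress the six-month ranks on the baseline ranks, and compare the residuals between arms by a t test (28 df). Both tests use ranks only, so the results hold for any monotone transformation of normal scores.

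| Power at d = 0.62 | r = 0 | 0.3 | 0.5 | 0.7 | 0.8 |
|---|---|---|---|---|---|
| Mann-Whitney, post only | 36% | 36% | 36% | 36% | 36% |
| Rank-ANCOVA | 35% | 37% | 43% | 56% | 69% |

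With the continuity correction, Mann-Whitney power is 34-35%. With heavily tied scales (five assumed sets of cut points), Mann-Whitney power is 27-35% and rank-ANCOVA power is 29-36%, 31-41%, 36-52% and 41-63% at latent r = 0.3, 0.5, 0.7 and 0.8.

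**4. False positives with no effect.** A baseline gap above one standard error means a difference above √(2/15) = 0.365 SD, which occurs in 32% of samples.

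| False-positive rate | r = 0.3 | 0.5 | 0.7 | 0.8 |
|---|---|---|---|---|
| Mann-Whitney, all samples | 5% | 5% | 5% | 5% |
| Mann-Whitney, gap above 1 SE | 7% | 9% | 12% | 14% |
| Mann-Whitney, other 68% | 4% | 3% | 2% | 1% |
| Rank-ANCOVA, either subset | 5% | 5% | 5% | 5% |
| Either test significant, all samples | 6.4% | 7.1% | 8.1% | 8.5% |

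Check at r = 0.7: 0.32 × 0.122 + 0.68 × 0.018 = 0.051.

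**5. Range restriction.** Entry limits (FMA below 55, MAS 1 to 4) narrow the baseline and would lower r. With r′ = r√v/√(r²v + 1 − r²), where v is the variance of a standard normal cut off above, removing the top 10% (v = 0.712) or 25% (v = 0.535) turns r = 0.5 into 0.44 or 0.39, and r = 0.7 into 0.64 or 0.58. The cut-off fractions are assumed.

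**The case against.** The strongest case against the point has four parts.

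- **The loss is conditional.** A reader might infer that precision was certainly lost. The documents give no r, and below about 0.3 adjustment gains nothing useful. The entry limits, and the injection and six months of rehabilitation between the two measurements, could all weaken r, perhaps most for MAS. This stands, and the point is worded accordingly.
- **The planned test is valid.** A reader might infer from the 7-14% figures that its error rate is inflated. It is not: it averages 5%, and the documents report no baseline imbalance. This stands too.
- **The remedy cannot rescue the trial.** Also correct. Even at r = 0.8, rank-ANCOVA power is 69%, below 80%. As claims must still rest on the original tests, the power to claim stays at about 36%, and would be 31-33% if both tests had to agree.
- **Non-normality rules out adjustment.** This fails for the rank method, which needs only ranks, handles ties and keeps to the plan's non-parametric approach.

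A reader might also infer that the conclusion about mirror therapy rests on the within-arm Wilcoxon tests. The documents do not say so.

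**Conclusion.** The point holds as a conditional fault of efficiency. The documents establish that no between-arm test adjusts for a baseline taken before allocation, and that only 15 per arm were analysed. Whether this cost anything depends on r: negligible below about 0.3, clear from 0.5 (12% off the confidence interval and about 7 points of rank-test power), and large at 0.7 to 0.8 (27-39% and about 20 to 33 points). These sizes assume latent normal scores, a constant shift of d = 0.62 and the stated r values.

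The documents do not support calling the planned test invalid, assuming that an imbalance occurred, or expecting adjustment to restore 80% power. Nor would adjustment repair the exclusion of 13 of 43 randomised patients: a baseline gap among the 30 analysed need not be due to chance. This is a cheap improvement worth making, and it ranks behind the sample size and the exclusions.

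**What to change.** Add to the report, beside the original tests and whatever they show:

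- For MAS, both Brunnstrom scores, FMA-UE and paretic grip: a six-month between-arm rank-ANCOVA adjusted for the same measure at baseline.
- For FMA-UE and paretic grip: the ANCOVA-adjusted mean difference with 95% CI, as the effect estimate.
- For MAS and Brunnstrom, where rank-ANCOVA yields no effect estimate: category counts by arm at both times.
- The observed r for each scale, so that the reader can see whether adjustment mattered.

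Label all of these post hoc sensitivity analyses, since follow-up is complete. State that claims still rest on the original tests, so the power to claim an effect is not raised. What is gained is the narrower interval for two outcomes and, for every scale, a between-arm p-value whose error rate hardly depends on the baseline gap. Draw the conclusion about mirror therapy from between-arm results, because both arms received BTX-A and rehabilitation and within-arm change cannot separate the two.

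**Cost.** Five rank-ANCOVAs, two ANCOVA estimates and tables for three scales, on data already collected. If r is near zero, they cost up to 1 point of power and a 2% wider interval. They also add tests to a set with no multiplicity correction: with two tests per outcome, the chance that either is falsely significant is about 6-9% at r = 0.3 to 0.8. An adjusted result alone must therefore not support a claim.

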Study Design and Participants

This study was conducted as a randomized, sham-controlled, single-blind clinical trial to investigate the combined effects of Botulinum Toxin Type A (BTX-A) and Mirror Therapy (MT) on upper extremity spasticity in stroke patients. Ethical approval was obtained from the Institutional Review Biruni University Clinical Research Ethics Committee and all participants provided written informed consent prior to enrollment in accordance with the Declaration of Helsinki (2015-KAEK-80 23 50).

Participants were selected from the neurological rehabilitation clinic of the physical medicine and rehabilitation unit at Biruni University Hospital. Eligible patients were those diagnosed with unilateral ischemic stroke and scheduled to receive BTX-A injections for upper extremity spasticity management.

Inclusion criteria were as follows:

- Age \geq 18 years
- Diagnosis of unilateral ischemic stroke confirmed by neuroimaging (MRI or CT)
- At least 3 months post-stroke to ensure chronic phase status
- Routine follow-up under the care of the same clinician who determined BTX-A treatment indication based on established clinical guidelines
- Mini-Mental State Examination (MMSE) score > 24 to ensure adequate cognitive function for participation
- Fugl-Meyer Assessment (FMA) upper extremity motor score < 55 , indicating moderate to severe motor impairment
- Modified Ashworth Scale (MAS) score between 1 and 4 in the affected upper extremity, indicating presence of spasticity

Exclusion criteria:

- Prior BTX-A or other neurotoxin injections to the affected upper extremity within the last 6 months
- Severe cognitive impairment or psychiatric disorders interfering with communication or compliance
- Concurrent participation in other experimental rehabilitation or pharmacological trials

- Visual or motor deficits severe enough to prevent effective engagement with Mirror Therapy
- History of multiple strokes or bilateral brain lesions
- Presence of neuromuscular diseases affecting the unaffected upper extremity
- Stroke etiology other than ischemic (e.g., hemorrhagic stroke, traumatic brain injury)

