Following BTX-A injection, all participants in both groups underwent a standardized conventional upper extremity rehabilitation program for a duration of 6 months, with sessions conducted three times per week. The rehabilitation protocol included stretching exercises, passive and active-assisted range of motion exercises, coordination and balance training, as well as functional task-oriented activities. All sessions were conducted in a one-on-one setting by experienced physiotherapists.

Experimental Group (Group I): Mirror Therapy Application

In the experimental group, mirror therapy (MT) was administered in addition to conventional rehabilitation. The MT protocol was implemented as follows:

- Participants were seated upright with a large mirror placed in the midsagittal plane of the body, such that the reflection of the non-paretic extremity appeared to replace the paretic extremity.
- Movements were performed with the non-paretic extremity while patients observed the mirrored image, creating the visual illusion that the paretic extremity was moving.
- Mirror therapy was applied three times per week, with each session lasting 30 minutes, for a total of 60 sessions.
- Exercises included functional movement patterns such as finger flexion and extension, thumb abduction–adduction, and thumb opposition movements, as well as wrist flexion/extension, forearm pronation/supination, elbow flexion/extension, and simple grasp-and-release activities.

- The sequence of movements was progressively adapted to the participant's functional level, starting with isolated distal motions (finger and thumb exercises) and advancing toward combined and proximal joint movements (wrist and elbow). Patients were continuously encouraged to focus on the mirrored image to reinforce the visual illusion of symmetrical movement.

Control Group (Group II): Sham Intervention

The control group received a sham intervention designed to mimic the physical setup of mirror therapy but without inducing the visual illusion:

- A transparent glass panel was used in place of a mirror, and participants were asked to observe the reflection of their paretic extremity directly through the glass.
- This setup was intended to replicate the environment of MT without stimulating the motor cortex through visual feedback.
- The frequency, duration, and total number of sessions matched those of the experimental group (3 sessions/week, 30 minutes per session, 60 sessions in total).

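### Pre-to-post change is tested only within each arm, over a window both arms share with BTX-A and rehabilitation; the between-arm test ignores baseline

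*Combined protocol and SAP*

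**What the plan says.** Two tests bear on this point, both in the Statistical Analysis section. Change over time is handled within arms: "To evaluate within-group changes from pre- to post-treatment, the Wilcoxon signed-rank test was used". The arms are compared on scores at each time point separately: "Between-group comparisons at baseline and post-treatment were conducted using the Mann-Whitney U test for continuous variables". Spearman coefficients correlate the changes with each other but do not compare the arms. One threshold covers everything: "A two-tailed p-value < 0.05 was considered statistically significant for all analyses". No sentence says which test decides whether mirror therapy works, although the sample size paragraph speaks of differences between groups.

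Evaluation Criteria fixes the window: "Treatment efficacy was assessed at two time points: baseline (prior to BTX-A injection) and six months post-injection". Study Design and Participants gives the order of events: "Following baseline evaluations and BTX-A injections, participants were randomly allocated into two groups". Intervention Protocol adds a second shared treatment: "all participants in both groups underwent a standardized conventional upper extremity rehabilitation program for a duration of 6 months". The end of that section starts rehabilitation and the mirror or sham sessions together, two weeks after injection. The arms differ by design only in mirror versus transparent panel.

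**The concern.** The quantity tested within each arm is the combined result of BTX-A, conventional rehabilitation, the passage of time and the mirror or sham sessions. Only the last of these differs between the arms. A small p-value in the mirror arm is compatible with mirror therapy adding nothing, and a within-arm test has no randomised comparator to separate the components.

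The plan tests change nowhere else. A reader who wants to know whether patients improved more with the mirror has two within-arm p-values to set side by side and one between-arm test that takes no account of where each patient started. Reporting significance in one arm and not in the other as a treatment effect is a well-known error, and the plan contains nothing that rules it out. At stake is whether a conclusion about mirror therapy rests on the randomised comparison.

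**Working it through.** **Inputs.** From the documents: 15 analysed per arm ("15 participants in each group (n = 30 total) completed the full 6-month intervention and follow-up assessments"), Wilcoxon signed-rank within each arm, Mann-Whitney between arms, two-sided 0.05. The documents give no expected common change, so it is assumed, in SD units of the change score, and varied. Change scores are taken as normal. The plan states no figure for within-arm change, so there is none to reproduce.

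**Step 1: what the within-arm test measures.** Baseline precedes the injection, and randomisation follows it. BTX-A and conventional rehabilitation both fall inside the window in both arms. If mirror therapy does nothing, the expected change is the same non-zero value c in both arms, and the Wilcoxon test will detect it with some power p.

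**Step 2: how often the misleading pattern arises.** With the same c in two independent arms,

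P(mirror arm significant, sham arm not) = p × (1 − p),

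which is largest at p = 0.5, where it equals 0.25. Simulated per-arm power (20,000 trials per setting, rounded) gives:

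| Assumed common change c (SD) | Per-arm power p | p × (1 − p) |
|---|---|---|
| 0.25 | 0.14 | 0.14 × 0.86 = 0.12 |
| 0.4 | 0.29 | 0.29 × 0.71 = 0.21 |
| 0.55 | 0.49 | 0.49 × 0.51 = 0.25 |
| 0.8 | 0.80 | 0.80 × 0.20 = 0.16 |
| 1.0 | 0.94 | 0.94 × 0.06 = 0.06 |
| 1.2 | 0.99 | 0.99 × 0.01 = 0.01 |

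Counting the pattern directly in the simulated trials gives the same values to within about one percentage point. The rates are per outcome. Evaluation Criteria lists up to six measures: Brunnstrom hand and upper extremity, MAS, FMA-UE, and grip on the paretic and non-paretic sides.

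The risk changes form as c grows. At 1.2 SD the one-arm pattern is rare, but both arms are significant in about 97% of null trials, so nearly every trial of an inert mirror would show a significant improvement in the mirror arm.

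**Step 3: the between-arm alternative.** In the same null trials, Mann-Whitney on change rejects in 4-5% at every c, because the common change cancels.

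**Step 4: what ignoring baseline costs.** Take the plan's own d = 0.62 as a between-arm difference in SD of the six-month score, with 15 per arm, normal scores and equal variances. The pre/post correlation is assumed, since none is given (4,000 trials per setting):

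| Assumed pre/post correlation | Mann-Whitney, post score | Mann-Whitney, change | Rank ANCOVA on baseline |
|---|---|---|---|
| 0.3 | 35% | 26% | 38% |
| 0.5 | 35% | 34% | 43% |
| 0.7 | 34% | 53% | 57% |
| 0.85 | 35% | 81% | 79% |

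With no effect, all three reject in about 4-5% of trials. Rank ANCOVA has more power than the post-score test at every correlation tried. The raw change score has less power than the post-score test below a correlation of about 0.5.

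**The case against.** The strongest reply is that the plan does not make the error described. It uses the Wilcoxon test for what that test does, gives a randomised between-arm test at post-treatment, and bases its sample size on differences between groups. This stands. A reader might infer that the plan relies on the Wilcoxon tests to prove a mirror-therapy effect, or that it has no valid between-arm test. The documents support neither reading. Comparing six-month scores between randomised arms controls the type I error; omitting baseline costs precision and leaves chance imbalance unadjusted. (Restricting the analysis to 30 of 43 randomised patients is a separate matter that affects any between-arm test.)

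The reply also limits the size. One might count every trial in which exactly one arm is significant, which is 2p(1 − p) and reaches about 50%. Half of those are sham-only results, which nobody would read as mirror benefit. Nor is the rate always far above 5%: it falls to about 6% at 1.0 SD and 1% at 1.2 SD. Normal change scores are also only a rough stand-in for Brunnstrom and MAS grades, which are ordinal and heavily tied.

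Finally, a reader might add spontaneous post-stroke recovery to the shared causes. The plan calls its entry window chronic ("At least 3 months post-stroke to ensure chronic phase status") and gives no recovery rate, so this is inference. The point stands on BTX-A and rehabilitation alone.

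What the reply does not answer is that the plan never calls the within-arm tests descriptive, gives them the same threshold as every other analysis, and names no between-arm analysis that uses baseline.

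**Conclusion.** The point holds as one of attribution and of an incomplete between-arm analysis. Within-arm p-values over this window carry no information specific to mirror therapy. If they were compared across arms, the mirror-only pattern would appear in about 12-25% of null trials per outcome for common changes of 0.25 to 0.8 SD, and in 6% and 1% at 1.0 and 1.2 SD. These rates rest on normal change scores, 15 per arm and assumed values of the common change, and they describe a decision rule that the plan does not state. The post-treatment Mann-Whitney test is valid but leaves the baseline unused. Severity: should fix.

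The attribution argument does not depend on the exact length of the window, but the documents need reconciling there. Six months of rehabilitation that begins two weeks after injection does not fit before an assessment at six months. Enrolment to February 2025 with all evaluations complete by March 2025 leaves no six-month follow-up for late enrollees.

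**What to change.** 1. State that the efficacy of mirror therapy is judged only on the between-arm comparison.
2. Make that comparison baseline-adjusted. One option is a rank-based ANCOVA of the six-month score on baseline. Where differences are meaningful, as for FMA-UE and grip strength, Mann-Whitney on change with a Hodges-Lehmann difference and 95% confidence interval is another. Fix the choice before re-running. The first is safer when the pre/post correlation is unknown, and it avoids subtracting ordinal grades.
3. Label this analysis as added after data collection, and report the planned post-treatment Mann-Whitney result beside it.
4. Keep within-arm change as description, without efficacy p-values, and say that it reflects BTX-A, rehabilitation, time and the mirror or sham sessions together.

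The cost is a few sentences and a short re-analysis of data already held; no new patients or visits are needed. The downsides are the post hoc label and the loss of the within-arm p-values.

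### The Spearman correlations between change scores do not say how arm is handled; if the arms are pooled, a treatment effect on two outcomes would by itself correlate them

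*Combined protocol and SAP*

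**What the plan says.** The Statistical Analysis section links most of its tests to a comparison. Mann-Whitney and Chi-square tests are for differences between groups, and the Wilcoxon signed-rank test is for change within a group. The correlation sentence carries no such label. It says only that Spearman's coefficient "was calculated to assess the relationships between changes in motor function, spasticity, and muscle strength". No split by arm, covariate or partial correlation is mentioned there or elsewhere.

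The next sentence covers the correlations as well: "A two-tailed p-value < 0.05 was considered statistically significant for all analyses". There is no multiplicity adjustment: "No corrections for multiple comparisons were applied, as the primary outcomes were pre-specified".

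The analysed set is described under Study Design and Participants: "15 participants in each group (n = 30 total) completed the full 6-month intervention and follow-up assessments". Under Evaluation Criteria, outcomes are measured at baseline and six months, so each patient has one change score per outcome.

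**The concern.** Arm is a common cause of both change scores whenever the treatment affects both outcomes. A coefficient over all participants then combines two things: how the changes go together among patients treated alike, and how far apart the two arms lie on both scales. The first says whether patients whose spasticity fell more also gained more function. The second says only that one arm did better on both, which the between-group tests already address. A significant rho could be taken for the first when it reflects the second.

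Randomisation does not protect against this, because the randomised arm is itself the source. Calling the correlations exploratory would soften the claim but leave the coefficient unchanged.

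**Working it through.** **Plan's own figures.** The plan states no figure for the correlations, so there is none to reproduce. From its sample-size paragraph I take d = 0.62. (The total of 28 given there does not follow from d = 0.62: a two-sided two-sample t-test at 80% power needs 42 per arm, 84 in all. That is a separate matter, and nothing below depends on it.)

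**Inputs.** 15 per arm and two-sided 0.05, from the documents. My assumptions are normal change scores with SD 1 in each arm, zero correlation between the two changes within each arm, and effect sizes other than 0.62, shown as a range.

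**Formula.** With equal arms the arm indicator has variance 1/4. Shifts d1 and d2 add d1 × d2/4 to the pooled covariance, and d1²/4 and d2²/4 to the pooled variances. The correlation induced by arm alone is

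r = (d1 × d2/4) / √[(1 + d1²/4)(1 + d2²/4)],

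which for equal shifts is (d²/4)/(1 + d²/4). At d = 0.62 this is 0.0961/1.0961 = 0.088. At d = 1.1 it is 0.3025/1.3025 = 0.232.

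**Simulation** (20,000 replicates per row, equal shifts):

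| d on both outcomes | r by formula | mean pooled rho | pooled test, p < 0.05 | arm-adjusted test, p < 0.05 |
|---|---|---|---|---|
| 0.3 | 0.022 | 0.022 | 5.5% | 5.3% |
| 0.62 | 0.088 | 0.088 | 7.7% | 5.1% |
| 0.8 | 0.138 | 0.136 | 11.2% | 4.9% |
| 1.0 | 0.200 | 0.203 | 19.3% | 5.3% |
| 1.11 | 0.235 | 0.241 | 25.3% | 4.9% |
| 1.5 | 0.360 | 0.381 | 57.3% | 4.8% |

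Repeat runs gave 7 to 8% at 0.62 and about 25% at 1.1. For scale, about d = 1.1 is what 13 + 15 patients could detect with 80% power.

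**Variations.**
- One outcome shifted (1.5 and 0): mean pooled rho -0.002, rejection 5.3%.
- Unequal shifts (0.62 and 0.3): 0.0465/√(1.0961 × 1.0225) = 0.044, rejection about 5.6%.
- Opposite signs (1.0 and -1.0): mean pooled rho -0.201, rejection 19%. Lower MAS and higher FMA-UE are both better, so the artefact for that pair would be negative.
- Changes cut to three levels, as a rough stand-in for the ordinal scales, at d = 1.1: rho about 0.21, rejection about 20%.

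**Precision of the alternatives.** The smallest |rho| that reaches p < 0.05 is t/√(df + t²).
- One arm of 15: df = 13, t = 2.160, giving 0.51.
- Arm-adjusted over 30: df = 27, t = 2.052, giving 0.37.
- Pooled over 30: df = 28, t = 2.048, giving 0.36.

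**The case against.** The strongest objection is that the text never says the arms were pooled. It follows a sentence about within-group change, opens as an addition to it, and speaks of relationships in the plural, so calculation by arm is compatible with it. If that was done, the artefact does not arise. This stands: a reader might infer that the reported correlations are biased, and the documents do not establish that. They leave the method open, and pooling is only the more natural reading because the neighbouring sentences name their grouping and this one does not.

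Second, the plan does not say which association it wants. With one change score per patient, any rho here is an association across patients, and one over all treated patients is a legitimate description. Calling the extra rejections false positives presumes that the within-arm association is the target. That also stands. But the plan should then say so, because the two quantities support different conclusions.

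Third, the distortion is modest at the only documented effect size and shrinks further with unequal shifts. Normal data are a simplification, since the plan reports non-normality and uses coarse scales. Both points are right. Coarsening weakened the effect without removing it.

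Finally, a reader might conclude that significance tests on these correlations should be dropped. Confounding by arm does not imply that, since the arm-adjusted test holds about 5%.

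**Conclusion.** The point holds as a gap in specification with a conditional bias. If rho was computed over all 30 participants, a treatment effect on both outcomes induces a correlation with no association inside either arm. Its size depends on the between-arm effects: minor at d = 0.62, and material only at effects of around 0.8 and above, which are assumed here and not taken from the plan. Both outcomes must differ between arms. Improvement common to both arms, for example from the BTX-A injections that everyone received, does not produce it.

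The weight is low. This is a secondary analysis, and the Mann-Whitney comparisons between groups are untouched. It is worth correcting because the remedy is cheap and readers cannot otherwise tell which association a reported rho describes.

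**What to change.** Compute each correlation as a partial Spearman coefficient adjusted for arm, report rho with a 95% confidence interval, and state in the Statistical Analysis section that this was done. By-arm coefficients may be added as description, with a note that 15 patients per arm give wide intervals.

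No new data are needed. In SPSS it means ranking the change scores and then running a partial correlation with arm as the control variable. The statistical cost is one degree of freedom, which moves the significance threshold for |rho| from about 0.36 to 0.37. Relying on by-arm values alone would raise it to about 0.51, so the adjusted coefficient should be the main result.
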